10.1 Primary objective

The primary objective is to show that the cure rate after local application of test product **sector** is better than a predefined limit. It has to be shown, that the test product **sector** achieves a cure rate superior to 70% (cure rate at the end of day 10, corrected for re-infestation).

Hereby, the following primary endpoint is investigated:

 Cure rate at the end of day 10 (corrected for re-infestation) for the test product for all baseline infestations

10.2 Secondary objectives

Secondary objectives refer to comparison of the cure rate of test product **GOLDGEIST**[®] FORTE using the following endpoints:

Secondary endpoint: Difference of cure rates (as defined as primary endpoints).

Secondary efficacy objectives:

- 2. To show that the cure rate at the end of day 10 (corrected for re-infestation) for the reference product GOLDGEIST[®] FORTE for all baseline infestations is better than 70%
- 3. To show that the test product **Exercise** has a cure rate superior to that of the reference product GOLDGEIST[®] FORTE

4. In case that superiority cannot be shown: to show that the test product **Exercise** is non-inferior to reference product GOLDGEIST[®] FORTE regarding cure rate. Thereby a non-inferiority margin of 7.5% will be used.

Further secondary objectives refer to objectives 3-4, however evaluated in subgroups or other time points.

- 5. Efficacy of the investigational products for head lice for mild and moderate baseline infestations (cure rate at the end of the study day 10, corrected for re-infestation)
- 6. Efficacy of the investigational products for head lice for all baseline infestation (cure rate at day 1)
- 7. Efficacy of the investigational products for head lice for mild and moderate baseline infestations (cure rate at day 1)

As further secondary objectives, safety and tolerability of test product **GOLDGEIST**[®] FORTE as well as the acceptance of the investigational products will be evaluated.

Secondary safety objectives:

- 8. To evaluate local tolerability by patient: subjective symptoms (burning, paraesthesia, pruritus): 0h, 1h, 24h, 7d and 10d p.a. (descriptive evaluation)
- 9. To evaluate global tolerability by the patient and study staff (number of subjects with global tolerability ratings of "very good", "good", "moderate", "poor", descriptive evaluation) at 10d after application
- 10. To evaluate skin irritation by study staff (secondary infection, erythema, excoriation) on day 0, 1, 7 and 10
- 11. To evaluate eye irritation by study staff on day 0, 1, 7 and 10
- 12. To evaluate characterisation of safety and tolerability of the investigational products considering Adverse Events in the study population

11 Study design

This single-centre, randomised, controlled, investigator-blinded, comparative study will be conducted in 100 patients (female and male patients, \geq 1 year of age) with confirmed diagnosis of head lice infestation. The patients will be randomised in a 1:1 ratio on both treatment arms.

In this study a repeated treatment, as recommended in literature [20] will be performed. For twotreatment protocols it is recommended that the second treatment should be applied on day 7 to day 9 and the final assessment should be on day 10.

Both investigational products will be tested as given in the product leaflets in compliance with the above mentioned treatment recommendations.

Patients complying with the in- and exclusion criteria will receive the study medication according to a patient number, allocated in ascending order in correspondence with their inclusion into the study.

Treatment will be performed as described in chapter 15.4 (Administration of the investigational products). The member of the study staff who will administrate the treatment will be un-blinded because administration procedure, smell, consistency and colour of pediculicides differ. In any case, the member of the study staff performing the subsequent assessments (assessor) will be blinded.

After informed consent procedure, confirmation of the diagnosis, check of exclusion and inclusion criteria and randomisation the first administration of the investigational products will be performed by the study staff. At the next visit (24 hours p.a.) patients will be re-inspected for living lice, as well as for safety assessments.

On study day 7, after re-inspection for living lice the second administration with the same investigational product as in Visit 1 will be performed by the un-blinded study staff.

On study day 10 the final visit will be performed at the study centre for final assessments of tolerability and efficacy, performing the procedures listed in the general trial flow chart (see chapter 3). In case of a treatment failure or a re-infestation the patient will be referred to his/her practitioner.

12 Investigational products

12.1 Selection of doses in the study

In this study the individual dose is chosen, according to the leaflet or the instruction of use, depending on the length of the scalp hair.

For treatment with test product **Example** the hair and scalp should be covered completely with the product.

For the treatment with the reference product GOLDGEIST[®] FORTE patients with short hair will receive approximately 25 mL, while patients with hairs reaching the subject's shoulder will receive up to 35-40 mL. Patients with hairs from the subject's shoulder until the mid-back hair will be treated with about 75 mL of the investigational product. Infants will be treated with a maximum amount of 25 mL.

No more of the investigational products will be used, as necessary to properly cover the hair and scalp.

The time span of exposure to the investigational products on the uncovered hair will not exceed 10 (+ 2) minutes for the test product and 30 - 45 (+ 5) minutes for the reference product GOLDGEIST[®] FORTE as recommended in the instructions for use.

The corresponding amount of the investigational products will be evenly dispensed in dry hair over its full length, with special diligence on the base of the hair near the scalp. The applied amount of both investigational products will be documented for each patient in the CRF.

12.2 Identity of the investigational products

The investigational test product **supplied** is supplied by Oystershell Laboratories. The following samples of the investigational products have been chosen for the study:

	Test	Reference
Product name		GOLDGEIST [®] FORTE
Manufacturer	Oystershell Laboratories	Eduard Gerlach GmbH
Formulation	Shampoo	Solution
Active ingredient		Pyrethrum extract 0.3 g/100 g (Extract of Chrysanthemum cinerariaefolium blossoms (1:2,5), adjusted to 25 % pyrethrins with
		isoparaffin, extracting agent: 1) n-hexan 2) methanol/isoparaffin)
Packaging	100 mL	250 mL
Batch No.	NA	NA
Excipients		5-[2-(2-Butoxyethoxy) ethoxymethyle]-6- propyle-1,3-benzodioxole (Piperonylbutoxide)0.7 g/100 g
		Chlorocresole0.9 g/100 g Diethylenglycole40.0 g/100 g
		Sodium-Laurylethersulfphate-Solution 27 %
		Purified Water 2-Propanole, Caprylocaproyl Macrogolglycerides, Isoparaffin (C13-C14), Perfume, Quinolone yellow E 104, Phosphoric acid.
Licence No.	NA	6495154.00.00

TT 1: Pharmaceutical information on investigational products

12.3 Packaging and labelling

The investigational test product **mattern** will be provided, packed by and labelled by Oystershell Laboratories. The reference product GOLDGEIST[®] FORTE will be purchased from the market and will be used unchanged in the study.

All investigational products are to be stored in a locked area. Both investigational products have to be stored at room temperature; GOLDGEIST[®] FORTE has to be stored light protected.

12.4 Drug accountability

The use and fate of investigational products must be documented. After completion of the study, the containers including any remaining investigational product will be orderly destroyed by CardioSec GmbH.

A written explanation regarding the disposition of missing products or their containers is required.

13 Justification of the study

13.1 Risks related to the participation of the clinical trial

13.1.1 Procedure related risks

There is no procedure related risk identifiable.

13.1.2 Risks related to the investigational drugs

13.1.2.1 Test product

The test product has been marketed since 2009 in 40 countries under the brand name Silcap lice shampoo or Paranix. After treatment with Silcap shampoo the following adverse effects were reported in a previous clinical trial [21]:

- Mild transient burning sensation and redness of the face skin.
- Mild transient burning sensation on the eye after contact to the shampoo

Warnings and safety information according to the leaflet of the medical device:

Do not use in case of hypersensitivity to mineral oils. In the case of a rash or signs of irritation/allergy, stop the treatment immediately. Do not use this product when the scalp is already very irritated or injured.

Make sure you rinse out the product well. Always respect the duration of the treatment (10 minutes). Do not use the product under occlusion, e.g. by covering up the hair with a cap or wrapped foil.

Avoid any contact with the eyes and mucous membranes (mouth and nose). If the product comes into contact with the eyes, rinse out thoroughly with water.

For external use only. In case of accidental ingestion contact a doctor or the anti-poison Centre.

Keep out of the reach of children.

Keep treated hair away from open fire. Do not smoke during treatment.

White mineral oil is no hazardous substance or mixture according to Regulation (EC) No. 1272/2008. This substance is not classified as dangerous according to Directive 67/548/EEC.

13.1.2.2 GOLDGEIST[®] FORTE

The investigational product GOLDGEIST[®] FORTE contains pyrethrum extract as the active ingredient.

The following Adverse Events are described in package information leaflet which have been reported after treatment with GOLDGEIST[®] FORTE:

very frequently	≥ 1/10
frequently	≥ 1/100 and ≤ 1/10
occasionally	≥ 1/1000 and ≤ 1/100
rarely	≥ 1/10000 and ≤ 1/1000
very rarely	\leq 1/ 10000 and single cases

Skin:

Rarely: local skin irritations, temporary itching and redness of the treated skin areas

Central nervous system and sense organs:

Very rarely: contact sensitivity

Warnings and safety information's:

Chlorocresol may produce an allergic reaction.

Contact with eyes, mucous membranes, sore skin or lesions should be prevented, as this could cause itching, irritation or burning of the skin and eyes. In case of accidentally contact the affected area has to be carefully rinsed with sufficient amount of clear water.

Do not use when the scalp is already very irritated or injured.

As stated in the exclusion criteria, no patient with known allergic reactions to the active ingredients used or to constituents of the pharmaceutical preparation with both IMPs, as well as chrysanthemum and other composite plants, will be included in this study.

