14.2 Exclusion criteria

A participant is not eligible, if any of the following exclusion criteria are present:

- 1. Known allergic reactions or hypersensitivity to the active ingredients used or the constituents
- 2. Patients with known skin allergies, multiple drug allergies or multiple allergies to cosmetic products
- 3. Pregnant or breast feeding women
- 4. Patient underwent treatment with any form of head lice treatment within the last 30 days prior to the Screening Visit (day 0)
- 5. Patients with chronic scalp disorder
- 6. Individuals on systemic or topical drugs or medications, including systemic antibiotics, which in the opinion of the investigative personnel may interfere with the study results
- 7. Subjects with hair longer than mid-back
- 8. Patients suspected or known not to follow instructions
- 9. Patients or his/her legal representative who are unable to understand the written and verbal instructions, in particular regarding the risks and inconveniences they will be exposed to as a result of their participation in the study
- 10. Previous participation in this study or participation in any other investigational trial within the preceding 30 days
- 11. The patients are investigator site personnel directly affiliated with this study and/or their immediate families. Immediate family is defined as a spouse, parent, child, or sibling, whether biological or legally adopted.
- 12. The patients are Oystershell employees or are employees of third-party organizations involved in the study.

The exclusion criteria are chosen to assure that patients with specific risks for administration of the investigated drug and patients with conditions that may have an impact on study parameters are excluded.

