14.3 Method of assigning volunteers to treatment groups

This study will be randomised and investigator-blinded. When patients will arrive at the site they get a screening number. After the patient or his/her legal representative will give his/her written informed consent the patients will receive the subject number. Each patient who meets the inclusion and exclusion criteria will be assigned the lowest yet unassigned random number available at the centre. Randomisation will be performed during the Screening Visit V01 on day 0.

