15.2 Study Visits and measures

15.2.1 Screening Visit V01 (day 0): study initiation, registration, enrolment, randomisation, first administration

Patients with suspicion of head lice infestation will be recruited for this study. Written informed consent will be obtained from adult patients or the legal representative of minors. Children able to read and write have to give their assent in written. The assent of younger children will be given verbally as far as appropriate.

Patient's eligibility for participation in the trial will be established by the investigator prior to enrolment.

Demographic data (gender, subject age, hair length (short, shoulder long, mid-back, long), medical history, PTSS during the last week prior to the intended administration of the investigational products, concomitant diseases and concomitant medication (especially chronic medications and use of medications including OTCs during the last 1 weeks, and use of anti-head lice treatments) will be recorded.

Body weight and height will be determined.

The diagnosis head lice infestation will be confirmed by:

• identification of at least five living lice or nymph (immature forms) and five live eggs

The study staff will examine the entire scalp and head hair as described in 15.5.6. Every part of the hair will be examined and the findings will be documented in the CRF:

The severity of head lice infestation will be judged on a 4-point severity scale:

- 0 = no relevant infestation (0-4 lice and/or nymph present);
- 1 = mild (5-9 lice and/or nymphs present);
- 2 = moderate (10-24 lice and/or nymphs present);

• $3 = \text{severe} (\geq 25 \text{ lice and/or nymphs present}).$

Patients will be considered eligible for participation in the study if they do meet any of the inclusion and none of the exclusion criteria. Patients will be received a subject number in ascending order.

In order to ensure administration and precise efficacy and tolerability assessments the patients will be housed at the study site until the assessments 60 minutes after the end of administration have been finished.

The investigational products will be applied at the centre by un-blinded either physicians or specially-instructed nursing staff (see 15.4.

Date and times of start and end of application of the investigational product and times of tolerability and efficacy assessments will be documented.

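### Section 13.1.2.2 says the exclusion criteria bar patients allergic to composite plants, but neither exclusion list contains that rule

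*Protocol*

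**What the plan says.** The risk section for the reference product (Protocol 13.1.2.2) begins its closing statement with "As stated in the exclusion criteria, no patient with known allergic reactions to the active ingredients used or to constituents of the pharmaceutical preparation" and ends it with "as well as chrysanthemum and other composite plants, will be included in this study". It presents the plant-allergy exclusion as something the criteria already contain.

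Exclusion criterion 1, in the same words in the synopsis and in section 14.2, reads "Known allergic reactions or hypersensitivity to the active ingredients used or the constituents". Criterion 2 adds known skin allergies, multiple drug allergies and multiple cosmetic allergies.

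The lists decide who is randomised. Section 14.3 states: "Each patient who meets the inclusion and exclusion criteria will be assigned the lowest yet unassigned random number available at the centre". Section 15.2.1 bases eligibility on the same criteria: "Patients will be considered eligible for participation in the study if they do meet any of the inclusion and none of the exclusion criteria" (presumably meaning all of the inclusion criteria). Section 14.2 gives the purpose of the list: "The exclusion criteria are chosen to assure that patients with specific risks for administration of the investigated drug", among others, are kept out.

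**The concern.** The protocol describes a safeguard in its risk narrative that its eligibility lists do not carry. Section 13.1.2.2 sets up no check of its own. It relies on the lists, and the item is missing from them. Staff who screen from section 14.2 or the synopsis could therefore correctly pass a patient whom section 13.1.2.2 says will not be enrolled.

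This is a participant-safety matter because the allergy concerns the reference product. Sections 8.1 and 13.1.4 both attribute the most common human problems with pyrethrum to its allergenic properties. Patients may be as young as 1 year, and the reference product stays on the scalp for 30 to 45 minutes per application. The ethics committee also votes on a document whose risk section credits the criteria with a protection they lack.

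**Working it through.** The protocol states no figure on this point, so the check is a comparison of texts.

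**Step 1: what is promised.** Section 13.1.2.2 names three grounds for non-inclusion: known allergy to the active ingredients, to the constituents, and to chrysanthemum or other composite plants. The third is joined as an addition to the first two, so the protocol itself treats it as more than ingredient allergy.

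**Step 2: what the lists contain.** The two lists hold the same 12 criteria.

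- Criterion 1: allergy to ingredients or constituents.
- Criterion 2: skin, multiple-drug and multiple-cosmetic allergies.
- Criteria 3 to 7: pregnancy or breast feeding, recent lice treatment, chronic scalp disorder, interfering medication, hair length.
- Criteria 8 to 12: compliance, understanding of instructions, other trial participation, and site or sponsor affiliation.

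Count naming chrysanthemum or composite plants: 0 of 12 in the synopsis and 0 of 12 in section 14.2. The inclusion criteria do not mention allergy either.

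**Step 3: what the existing criteria catch indirectly.**

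- *Chrysanthemum allergy.* Section 12.2 describes the active ingredient as an extract of chrysanthemum "blossoms (1:2,5), adjusted to 25 % pyrethrins with" isoparaffin. An investigator can reasonably read criterion 1 as covering it.
- *Skin allergy to any composite plant.* Criterion 2 covers this.
- *Non-skin allergy to composite plants other than chrysanthemum, with no known pyrethrum reaction.* No criterion covers this. Those plants are neither an active ingredient nor a constituent listed in section 12.2, a single plant allergy is not a multiple drug or cosmetic allergy, and it is not a skin allergy.

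**Step 4: consequence for a patient in that last group.** The patient passes every listed criterion and receives a random number under section 14.3. Section 11 states: "The patients will be randomised in a 1:1 ratio on both treatment arms". Hence P(reference product | enrolled) = 1/(1 + 1) = 50%. Two applications are planned, on day 0 and day 7. The second is withheld if the day 7 pre-treatment assessment shows severe skin or eye irritation, so exposure is at most two applications.

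**Step 5: how many patients.** The protocol gives no prevalence of composite-plant allergy, so no count among the 100 planned patients can be derived.

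**The case against.** The best reply is that the rule is in the protocol. Section 13.1.2.2 says without qualification that such patients will not be included, and section 15.2.1 has the investigator establish eligibility before enrolment. On this view a rule was simply not copied into two lists. The uncovered group is very small. The reactions that section 13.1.2.2 describes for the product are mainly cutaneous and rare or very rare, and criterion 2 already deals with known skin allergies. Nothing in the protocol shows that allergy to other composite plants predicts a reaction to this product. Harm is also limited by other measures: staff apply the product on site, patients stay until 60 minutes after administration, treatment is stopped and washed off if not tolerated, and section 15.8.1 requires emergency equipment and trained staff for anaphylactic shock.

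Much of this stands. The gap is narrow, its clinical size is not demonstrated, and the case report form is not shown and may already ask the question. Two parts do not stand. If section 13.1.2.2 binds on its own, the protocol contains two different eligibility rules, and one patient can satisfy the lists while being barred by the text. That needs correcting on either reading. And monitoring with rescue treatment does not replace an exclusion that the protocol says it applies.

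**Conclusion.** The inconsistency is real and the protocol is wrong as written: section 13.1.2.2 attributes to the exclusion criteria a rule that neither list contains, and the lists are the gate to randomisation. It should be fixed as a safety and consistency correction. It is a drafting inconsistency with no bearing on endpoint, sample size, power or error rates.

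Confidence is high for the mismatch in the text. The practical importance is modest and cannot be quantified from the protocol. The size of the remaining gap assumes that criterion 1 is read as covering chrysanthemum and that criterion 2 is applied to every known skin allergy. If criterion 1 were read more strictly, non-skin chrysanthemum allergy would fall into the gap as well.

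**What to change.** Extend exclusion criterion 1, in both the synopsis and section 14.2, with the phrase: or to chrysanthemum or other composite plants. The lists then say what section 13.1.2.2 claims they say. Confirm that the eligibility check at visit V01 asks about this allergy, and add the question if it does not.

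The cost is one phrase in two places and at most one allergy-history question. The only downside is possibly a few more screening failures, among patients the protocol already intends to exclude.

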13.1.3 Precautionary measures

Special precautionary measures are not considered to be necessary for this study. In case of emergency, standard emergency procedures will be employed. The Principal Investigator is to be consulted and informed immediately.

The Principal Investigator will provide all the necessary emergency equipment and specially trained staff to handle emergency events during this study.

All cases of emergency (e.g. occurrence of SAE (=Serious Adverse Event) and/or occurrence of increasing numbers of AE's (= Adverse Event), which will result in an unacceptable risk-benefit ratio) will be immediately reported to the project manager of CardioSec Clinical Research GmbH.

13.1.4 Risk/benefit evaluation

Test product **Constant** as well as the comparator GOLDGEIST[®] FORTE will be administered according to the instructions for use by the study staff.

White mineral oil, the active ingredient of test product **matrix** is no hazardous substance or mixture and is not classified as dangerous according. It has been used safely in a wide range of products (e.g. cosmetics, baby products, medications, lubricants). The test product **matrix** is only suitable for head lice (not public lice) and is recommended for children from 1 year of age and older.

Pyrethrin, the active ingredient of GOLDGEIST[®] FORTE, are used against a broad range of pests including ants, aphids, roaches, fleas, flies, ticks and also lice. They are available in dusts, sprays, and aerosol "bombs" and they may be mixed with synthetic pesticides or other natural products. They break down quickly, have a short residual, and have low mammalian toxicity, making them among the safest insecticides in use. However, they might cause allergic skin

reactions in some people. Overall, pyrethrins have low chronic toxicity to humans and the most common problems in humans have resulted from the allergenic properties of pyrethrum.

The reference product GOLDGEIST[®] FORTE is suitable for head lice, public lice and clothes lice and there are no age restrictions for usage.

Adverse events following administration of product or GOLDGEIST[®] FORTE will be monitored. Like in any trial, participating patients will be monitored during the assessment periods. No further special safety investigations will be carried out during the study as the investigational products known to be well tolerated.

The occurrence of severe drug related AE's is very unlikely after treatment with test and GOLDGEIST[®] FORTE.

After consideration of the benefits and risks, the performance of the study is considered ethically justifiable, as the expected future therapeutic benefits of the study preparation appear to be greater than the risks to the volunteers.

